6.8 Treatment Compliance

Subject compliance with study drug will be assessed by the investigator and/or study personnel at each visit using direct questioning, and pill counts. Deviations from the prescribed treatment regimen will be recorded on the source document and the subjects' eCRFs. All returned blister wallets or bottles must be reviewed at every visit while the subject is still at the clinic to

determine if the subject is dosing as instructed. Deviations from the prescribed treatment regimen will be recorded on the source document and the subjects' eCRFs.

During the Titration Period, if a subject misses a dose (or several doses), they should skip that dose and continue with the next scheduled dose. If a subject misses 7 or more consecutive days of dosing during the Titration Period, the site should contact the Sponsor or designee for guidance on how to proceed.

During the Double-Blind Treatment Period, a subject is said to be compliant if they have taken 80% to 120% of the expected tablets of study medication. If a subject has taken less than 80% or more than 120% of the expected tablets since the last visit, the subject should be counseled. In cases where noncompliance is continual, the site should contact the study Medical Monitor or designee to discuss other options, such as withdrawing the subject.

Compliance calculation has been defined in [Section 8.5](#).

7. VISIT SCHEDULE AND ASSESSMENTS

7.1 Study Procedures

The visit schedule and assessments are summarized in [Table 1-1](#).

7.2 Study Visits and Assessments

7.2.1 Visit 1 Screening (Day -28 to Day -1)

Screening of subjects will start at Visit 1 and continue up to 4 weeks prior to Baseline/Randomization (Visit 2) unless an extension is granted by the Medical Monitor in advance of the Visit 2. Screening procedures will include:

- Review study information with subject and obtain written informed consent
- Register subject in IWRS to receive Screening Number
- Review inclusion and exclusion criteria with the subject to determine the subject's eligibility
- Perform psoriasis assessments to ensure that subject will meet PASI, IGA, and BSA requirements at Baseline visit
- Collect medical history and demographic information
- Collect psoriasis medical history and use of all prior medications and non-drug therapies to treat psoriasis
- Review and record prior medications (used within the previous 30 days) and concomitant medications (medications currently used)
- Perform a complete physical examination, including height, weight, and waist circumference

- Measure vital signs (systolic and diastolic blood pressure, heart rate, and respiratory rate) with subject in a seated position
- Obtain a 12-lead ECG
- Obtain blood and urine samples for routine laboratory profile evaluations including hematology, serum chemistry, and urinalysis
- Obtain samples for serology: human immunodeficiency virus (HIV), hepatitis B virus surface antigen (HBsAg), antibodies to hepatitis B core antigen (anti-HBc), and hepatitis C virus (HCV)
- Obtain a sample for a serum pregnancy test for all female subjects. Instruct all female subjects to use approved form(s) of contraception
- Record any SAEs (from time of signing ICF)
- If subject meets the inclusion/exclusion criteria, instruct the subject to begin washout of prohibited medications and schedule Visit 2 pending receipt of lab and ECG results

7.2.2 Visit 2 – Randomization/Baseline (Day 0)

- Perform psoriasis assessments:
 - PASI, BSA, IGA
 - NAPSI for fingernails, PSSI, PP PGA for all subjects; if score is 0 at Baseline for any of these assessments, then the respective assessment(s) would not be required to be completed at future study visits
- Confirm psoriasis medical history and previous psoriasis therapies
- Confirm medical history and record any new findings
- Review and record medication changes since the Screening visit, including changes in prescription and OTC medications, herbal preparations, and vitamin and/or mineral supplements and non-drug therapies
- Confirm washout of prohibited medications
- Perform a partial physical examination with focus on previously noted abnormalities in organ systems, including skin
- Measure vital signs (systolic and diastolic blood pressure, heart rate, and respiratory rate) with subject in a seated position
- Obtain a 12-lead ECG (Baseline Visit central ECG reading will not be available prior to Randomization; Investigator must review Baseline ECG tracing to confirm eligibility prior to Randomization. Subject with clinically significant ECG findings in the Investigator's opinion will be screen failed. Investigator also must review the central ECG reading when results are available. Subjects with unacceptable ECG findings will be discontinued from the study)
- Review inclusion and exclusion criteria to confirm that the subject is qualified for study participation

- Perform a urine pregnancy test for female subjects of childbearing potential. Instruct all female subjects to use approved form(s) of contraception
- Obtain blood and urine samples for routine laboratory profile evaluations including hematology, serum chemistry, and urinalysis
- Blood collection for PD study as well as lymphocyte & Ab titer study
- Record any SAEs
- Have the subject complete the following assessments:
 - Pruritus NRS, DLQI, SF-12, QIDS-SR16, WPAI: PSO, HEOR
- Perform photography (at selected 3 sites only); see photography reference materials for details
- Randomize the subject in IWRS after confirmation of eligibility criteria
- Instruct subjects on dosing and dispense study drug
- Dispense educational materials for AE management (provided by Sponsor)
- Provide subject with Bristol Stool Chart; have the subject confirm the average frequency of their bowel movements for the past 15 days and the general consistency of the stool using the Bristol Stool Chart

7.2.3 Visit 3 (Week 4), Visit 4 (Week 8), Visit 5 (Week 12), Visit 6 (Week 16), Visit 7 (Week 20), and Visit 8 (Week 24)

- Review any concomitant medication changes since the previous study visit
- Perform a partial physical examination with focus on previously noted abnormalities in organ systems, including skin
- Measure weight
- Measure waist circumference (Week 24 only)
- Measure vital signs (systolic and diastolic blood pressure, heart rate, and respiratory rate) with subject in a seated position
- Record a 12-lead ECG
- Obtain blood and urine samples for routine laboratory profile evaluations including hematology, clinical chemistry, and urinalysis
- Blood collection for PD study
- Blood collection for lymphocyte subset & Ab titer study (Week 24, or at any time during the study if subject shows signs of PML)
- Perform a UPT for females of childbearing potential. Ensure that female subjects of childbearing potential are using approved method(s) of contraception.
- Record any AEs

- Perform psoriasis assessments if applicable:
 - PASI, BSA, IGA
 - NAPSI for target fingernail, if applicable (weeks 12, 16 and 24 only)
 - PSSI, PP PGA (if applicable)
- Have the subject perform the following assessments:
 - Pruritus NRS
 - DLQI, SF-12, QIDS-SR16, WPAI: PSO, HEOR (Weeks 12, 16, and 24 only)
- Perform photography (at selected 3 sites only) (Weeks 12, 16, and 24 only); see photography reference materials for details
- Assess IP compliance/accountability
- Dispense IP as applicable (Weeks 4, 8, 12, 16, and 20)

7.2.4 Early Termination Visit

- Review any concomitant medication changes since the previous study visit
- Assess IP compliance/accountability
- Perform a partial physical examination with focus on previously noted abnormalities in organ systems, including skin
- Measure weight
- Measure waist circumference
- Measure vital signs (systolic and diastolic blood pressure, heart rate, and respiratory rate) with subject in a seated position
- Record a 12-lead ECG
- Perform a UPT for females of childbearing potential. Ensure that female subjects of childbearing potential are using approved method(s) of contraception.
- Obtain blood and urine samples for routine laboratory profile evaluations including hematology, clinical chemistry, and urinalysis
- Blood collection for lymphocyte subset & Ab titer study
- Record any AEs
- Perform psoriasis assessments:
 - PASI, BSA, IGA
 - NAPSI for target fingernail, PSSI, PP PGA (if applicable)
- Have the subject perform the following assessments:
 - Pruritus NRS

- DLQI, SF-12, QIDS-SR16, WPAI: PSO, HEOR

7.2.5 Safety Follow-up Visit (Week 25 [+3 days], or 1 Week [+3 days] after ETV, unless final dose was taken >7 days prior to Week 24/ETV)

- Review any concomitant medications used since the previous study visit
- Perform a partial physical examination with focus on previously noted abnormalities in organ systems, including skin
- Measure vital signs (systolic and diastolic blood pressure, heart rate, and respiratory rate) with subject in a seated position
- Record a 12-lead ECG
- Perform a UPT for females of childbearing potential. Ensure that female subjects of childbearing potential are using approved method(s) of contraception.
- Record any AEs
- Perform psoriasis assessments:
 - PASI, BSA, IGA
 - NAPSI for the target fingernail , PSSI, PP PGA (if applicable)
- Have the subject perform the following assessments:
 - Pruritus NRS
 - DLQI, SF-12, QIDS-SR16, WPAI: PSO, HEOR

7.2.6 Unscheduled Visit

If a subject returns to the site for an unscheduled visit, the following assessments may be performed at the discretion of the Investigator:

- Review any concomitant medications used since the previous study visit
- Perform a partial physical examination with focus on previously noted abnormalities in organ systems, including skin
- Measure weight
- Measure vital signs (systolic and diastolic blood pressure, heart rate, and respiratory rate) with subject in a seated position
- Obtain blood and urine samples for routine laboratory profile evaluations including hematology, clinical chemistry, and urinalysis
- Record any AEs

7.3 Efficacy Assessments

Efficacy will be evaluated via psoriasis assessments and measures of QoL.

Psoriasis assessments include the PASI, the affected BSA, and the IGA. Subject-reported assessments of health-related QoL include the DLQI, 12-Item Short Form Survey (SF-12), the Quick Inventory of Depressive Symptomatology-Self Report (QIDS-SR), the WPAI:PSO, the HEOR, and the Pruritus NRS.

Other psoriasis assessments to be performed as applicable include the NAPSI for the target fingernail, the PSSI score, and the PP PGA score.

Brief descriptions of these assessments are presented as follows.

7.3.1 Co-Primary Efficacy Assessments: Psoriasis Area and Severity Index and Investigator's Global Assessment

The investigator or designee will assess the extent and severity of the subjects' psoriasis using the PASI scoring system and will perform a global assessment of disease severity using the IGA. The PASI scale is provided in [Appendix 1](#); the IGA is a 5-point scale which measures the investigator's or designee's impression of the disease at a single point. Assessments will be performed at the visits specified in [Table 1-1](#). Sites should make every effort to ensure consistency in evaluators across visits, especially between Baseline and Week 24.

Psoriasis Area and Severity Index

The PASI is a measure of the average redness, thickness, and scaliness of the lesions (each graded on a 0–4 scale) and weighted by the area of involvement ([Fredriksson, 1978](#)). There are a few validation studies performed describing, with some limitations, the construct validity, face validity, and sensitivity to change ([Ashcroft, 1999](#)). National Psoriasis Foundation Medical Advisory Board standardized the definitions of events of psoriasis recurrence based on PASI, including the definition of relapse, which is a loss of at least 50% of PASI improvement after discontinuation of treatment in patients who had achieved a clinically meaningful response; and rebound, which is PASI \geq 125% of Baseline or new generalized pustular, erythrodermic, or more inflammatory psoriasis ([Carey, 2006](#); [Gordon, 2005](#)). In the current trial, PASI improvement will be evaluated from Baseline to all visits during the Titration and Treatment Periods, and clinically meaningful response is defined as PASI-50 ([Carlin, 2004](#)).

Investigator's Global Assessment

The IGA should be performed by the same evaluator (rater) who performs the PASI assessments and all efficacy assessments should be performed by the same evaluator throughout the study when possible. The scale in [Table 7-1](#) will be used for the IGA assessment:

Table 7-1 Investigator's Global Assessment (IGA)

Score	Grade	Definition
0	Clear	No signs of psoriasis Post-inflammatory hyperpigmentation may be present
1	Almost clear	No thickening to minimal plaque elevation Normal to slight pink coloration/faint erythema Focal to minimal scaling
2	Mild	Slight elevation/thickening Pink to light red coloration Predominantly fine scaling partially or mostly covering lesions
3	Moderate	Clearly distinguishable/distinct thickening Definite red coloration Coarse scaling covering most plaques
4	Severe	Marked thickening with hard/sharp edges Bright to deep dark red coloration Thick/coarse scaling covering almost all or all lesions

Adapted from: Langley RGB, Feldman SR, Nyirady J, van de Kerkhof P, et al. The 5-point Investigator's Global Assessment (IGA) Scale: A modified tool for evaluating plaque psoriasis severity in clinical trials. *J Dermatolog Treat.* 2015;26(1): 23-31.

7.3.2 Secondary Efficacy Assessments

Secondary efficacy assessments will be performed at the visits specified in [Table 1-1](#).

7.3.2.1 Affected Body Surface Area

BSA will be calculated using handprint methodology, comparing the size of the affected area to the size of the subject's entire handprint, which equates to approximately 1% BSA. Evaluators should use the method consistently throughout the trial.

7.3.2.2 Nail Psoriasis Severity Index

The NAPSI is a numeric, reproducible, objective, simple tool for evaluation of nail psoriasis. This scale is used to evaluate the severity of nail bed psoriasis and nail matrix psoriasis by area of involvement in the nail unit. The NAPSI is provided in [Appendix 2](#).

7.3.2.3 Psoriasis Scalp Severity Index

The PSSI is a grading system for scalp psoriasis, which is similar to the PASI for generalized psoriasis. The scale for PSSI ranges from 0 (absent) to 4 (very severe) for each of the three categories of erythema, desquamation and thickness, which are rated separately. The individual scores are then added and multiplied by a number based on the area of the scalp that is covered by psoriasis. The final PSSI score can range from 0 to 72.

The PSSI is provided in [Appendix 3](#).

7.3.2.4 Palmoplantar Psoriasis Physician's Global Assessment (PP PGA)

The investigator or designee will assess the subject's palmar and plantar surfaces using the PP PGA score. The PP PGA is provided in [Appendix 4](#).

7.3.2.5 Pruritus Numerical Rating System

The subject will be asked to rate the intensity of their pruritus using the Pruritus NRS. The Pruritus NRS will be used to assess pruritus intensity over the previous 24 hours. It is a commonly used instrument with demonstrated high reliability and concurrent validity ([Phan, 2012](#); [Reich, 2009](#)). The NRS records the subject's perceptions of their pruritus and can be used to monitor changes over time.

7.3.3 Health-related Quality of Life Assessments

Health-related QoL assessments will be performed at the visits specified in [Table 1-1](#).

7.3.3.1 Dermatology Life Quality Index

The subject will be asked to complete the DLQI, which is a validated questionnaire consisting of 10 questions relating to the degree to which the subject's skin condition affects their daily activities ([Finlay 1994](#)). The DLQI is provided in [Appendix 5](#).

7.3.3.2 12-Item Short Form Survey

The SF-12 questionnaire contains a set of generic, coherent, and easily administered patient-reported quality-of-life measures that are useful for the monitoring and assessment of care outcomes in adult subjects. The SF-12 is provided in [Appendix 6](#).

7.3.3.3 Quick Inventory of Depressive Symptomatology-Self Report (16 Items)

The Quick Inventory of Depressive Symptomatology – Self Report is a questionnaire designed to be filled out by the subject to assess the severity of depressive symptoms. The Quick Inventory of Depressive Symptomatology – Self Report is provided in [Appendix 7](#).

7.3.3.4 Work Productivity and Activity Impairment Questionnaire: Psoriasis

The Work Productivity and Activity Impairment (WPAI) questionnaire is an instrument designed to measure impairments in work and in activities.

The Work Productivity and Activity Impairment Questionnaire: Psoriasis (WPAI:PSO) is provided in [Appendix 8](#).

7.3.3.5 Health Economics and Outcomes Research

The HEOR evaluation will be performed by asking three questions at Baseline, Week 12, Week 16, Week 24/ETV, and Week 25 Visit. The questions are the following:

- **Baseline visit**
 - How many times, in the past 3 months, have you been to any physician's office or urgent care clinic?
 - Please state reason for each visit
 - How many times, in the past 3 months, have you seen a nurse practitioner, a physician assistant, a psychologist, a naturopath, an acupuncturist, a chiropractor, or other healthcare professional (HCP)?
 - Please state reason for each visit
 - How many times, in the past 3 months, have you received care from a health professional in your home?
 - Please state reason for each visit
- **12 weeks, 16 weeks, 24 weeks and 25 weeks**
 - How many times, since you started the study medication, have you been to any physician's office or urgent care clinic, other than the regular assessment appointments as part of the clinical trial?
 - Please state reason for each visit
 - How many times, since you started the study medication, have you seen a nurse practitioner, a physician assistant, a psychologist, a naturopath, an acupuncturist, a chiropractor, or other healthcare professional (HCP)?
 - Please state reason for each visit
 - How many times, since you started the study medication, have you received care from a health professional in your home?
 - Please state reason for each visit

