4.2.2 Health Outcome/Quality of Life Endpoints

Change from Baseline in the following health outcome/QoL assessments at Weeks 12, 16, and 24:

- Quick Inventory of Depressive Symptomatology-Self Report (16 Items) (QIDS-SR16) total score
- DLQI total score
- SF-12 total score
- Work Productivity and Activity Impairment Questionnaire: Psoriasis (WPAI:PSO) score
- Health Economics and Outcome Research (HEOR) evaluation (see [Section 7.3.3.5](#))

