6.2 Dosing Regimen

Dosages and pill allocations for the Titration Period (Weeks 1-5) and for the Treatment Period (Weeks 6-24) are shown in [Table 6-1](#) and [Table 6-3](#), respectively. The dosing regimen for the Titration Period is presented in [Table 6-2](#). Note: Doses specified in red followed by a 'P' indicate Placebo.

Double-Blind Titration Period (Baseline through Week 5)

Following completion of the pre-randomization Screening Period, eligible subjects will be randomized in a 1:1:1:1 ratio to 1 of the 4 treatment arms and will enter the 5-week Double-Blind Titration Period. The first dose of study drug will be taken the day after the Baseline Visit (on Day 1). If a subject misses a dose (or several doses) during the Titration Period, they should skip that dose and continue with the next scheduled dose. At least 4 hours should elapse between doses, but ideally 8-12 hour intervals should be maintained. If a subject misses 7 or more consecutive days of dosing during the Titration Period, the site should contact the Sponsor or designee for guidance on how to proceed. At Visit 3 (Week 4), the subjects will

be instructed to continue 1 more week of Titration dose (Week 5 of blister wallets) and will also be given a kit of bottles which will allow dosing until Visit 4. Please refer to [Table 6-1](#) for titration schedule.

Double-Blind Treatment Period (Week 6 through Week 24)

Subjects will receive PPC-06 400 mg QD, PPC-06 400 mg BID, PPC-06 600 mg BID, or Placebo BID from Week 6 through Week 24, based on the treatment arm to which they were randomized. Subjects will return to the clinic every 4 weeks (± 3 days) thereafter for drug accountability and to undergo safety and efficacy evaluations per the schedule of assessments ([Table 1-1](#)).

- Visit 4: End of Week 8
- Visit 5: End of Week 12
- Visit 6: End of Week 16
- Visit 7: End of Week 20
- Visit 8: End of Week 24
- Visit 9: End of Week 25

Table 6-1 Treatment Schedule - Titration Period (Weeks 1-5)

	400 mg QD	400 mg BID	600 mg BID	Placebo BID
Week 1 (Days 1-7)	100 P (am) + 100 P (am) 100 P (pm) + 100 (pm)	100 P (am) + 100 P (am) 100 P (pm) + 100 (pm)	100 (am) + 100 P (am) 100 P (pm) + 100 (pm)	100 P (am) + 100 P (am) 100 P (pm) + 100 P (pm)
Week 2 (Days 8-14)	200 P (am) + 200 P (am) 200 P (pm) + 200 (pm)	200 P (am) + 200 P (am) 200 P (pm) + 200 (pm)	200 (am) + 200 P (am) 200 P (pm) + 200 (pm)	200 P (am) + 200 P (am) 200 P (pm) + 200 P (pm)

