### 12.7.3 Health-related Quality of Life Endpoints

The Health Outcome/Quality of Life endpoints are the change from baseline in the following health outcome/QoL assessments at Weeks 12, 16, and 24:

- Quick Inventory of Depressive Symptomatology-Self Report (16 Items) (QIDS-SR16) total score. The total score (range 0-27) is calculated as the sum of the following 9 items: Highest score on any sleep items (Q1-Q4), Q5, highest score on any appetite/weight items (Q6-Q9), Q10, Q11, Q12, Q13, Q14, highest score on either psychomotor items (Q15 & Q16). The total score will be considered as missing if any of the component score is missing.
- The Dermatology Life Quality Index (DLQI) total score (0-30) will be calculated as the sum of 10 questions with each ranging from 0 to 3. The scoring of each answer is as follows:

Very much	Scored 3
A lot	Scored 2
A little	Scored 1
Not at all	Scored 0
Not relevant	Scored 0
Question unanswered	Scored 0
Question 7: "prevented work or studying"	Scored 3

If one question is left unanswered this is scored 0 and the scores are summed and expressed as usual out of a maximum of 30. If two or more questions are left unanswered the total DLQI score is missing. If question 7a is answered 'no' or 'not relevant', then the answer of 7b will be ignored. Additionally, the score of each of 6 domains (daily activities, personal relationships, symptoms and feelings, leisure, work/school, and treatment) will be summarized separately.

- The SF-12 summary scales will be calculated using the SF-12 Health Survey Standard Scoring software. Summary scores will be computed for Physical Summary (PCS) and Mental Summary (MCS). Subscores will also be computed for the following 8 domains:
  - Physical Functioning (PF)
  - Role-Physical (RP)
  - Bodily Pain (BP)

- Social Functioning (SF)
  - Mental Health (MH)
  - Role-Emotional (RE)
  - Vitality (VT)
  - General Health (GH)
- Work Productivity and Activity Impairment Questionnaire: Psoriasis (WPAI:PSO) score. WPAI-PSO outcomes are expressed as impairment percentages, with higher numbers indicating greater impairment and less productivity, i.e., worse outcomes as follows
    - The percent work time missed due to psoriasis will be summarized for all subjects who answer “Yes” to Question 1, “Are you currently employed?”. This will be calculated using the following formula:  $100 * ((\text{Question 2}) / (\text{Question 2} + \text{Question 4}))$

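### HEOR visit counts cover a fixed 3 months at baseline but a growing period since first dose afterwards, so raw within-arm change and time course at Weeks 16 and 24 mainly reflect recall length

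*Protocol*

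**What the plan says.** Protocol 7.3.3.5 sets three count questions: physician or urgent care visits, contacts with other health professionals, and care at home. Each is followed by a request for the reason for every visit. At baseline the window is fixed: "How many times, in the past 3 months, have you been to any physician's office or urgent care clinic". At Weeks 12, 16, 24 and 25 it is cumulative: "How many times, since you started the study medication, have you been to any" (physician's office or urgent care clinic). The other two questions change window in the same way.

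Trial visits are treated unevenly. After baseline, the physician question tells the subject to leave out trial appointments. Its baseline version does not, and the other two questions never do.

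Protocol 4.2.2 defines the endpoint as "Change from Baseline in the following health outcome/QoL assessments at Weeks 12, 16, and 24" and lists "Health Economics and Outcome Research (HEOR) evaluation" among the items. SAP 12.7.3 does the same: the "endpoints are the change from baseline in the following health outcome/QoL assessments at Weeks 12, 16, and 24". SAP 11.3 computes change by plain subtraction unless otherwise specified.

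The planned output is narrower than that definition. Protocol 8.7.2 lists change from baseline for DLQI, SF-12, QIDS-SR16 and WPAI:PSO, and separately a by-visit summary for HEOR. The HEOR item in SAP 12.7.3 also plans a by-visit summary. The shell of Table 14.2.3.5 shows counts at baseline and Weeks 12, 16 and 24 with no change rows, and Listing 16.2.6.12 has no change column. SAP 12.8.3 makes all quality-of-life analyses descriptive, on the FAS.

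**The concern.** A count over 3 months and a count over 24 weeks are different quantities. Subtracting one from the other, or reading down a table that lists them one after another, mixes healthcare use with length of recall. Each later answer also contains the earlier ones, so the counts can only rise over time. Every arm, placebo included, would appear to use more care as the trial goes on, and a real reduction could be hidden.

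The health-related quality-of-life measures, with which HEOR is grouped, fall under the first secondary objective. What is at stake is whether the HEOR results can be read as a change or a course over time. The trial's main efficacy conclusion is not at stake.

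**Working it through.** The documents give no numerical target for HEOR, so there is no plan figure to reproduce.

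**Inputs**
- Baseline window B: 3 months (Protocol 7.3.3.5). In calendar terms this is 365.25 / 12 × 3 / 7 = 13.04 weeks. A subject may read it as 12 weeks, so both are shown.
- Post-baseline window w: 12, 16 and 24 weeks. It starts at first dose, which Protocol 6.2 places on the day after the Baseline Visit.
- Weekly visit rate r: not in the documents. Assumed constant, to isolate the effect of the wording.

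**Formulas**
- Baseline count = r × B; count at week w = r × w.
- Ratio to baseline = w / B, whatever the value of r.
- Change = r × (w − B).

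**Results under constant use**

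| Visit | Ratio, B = 13.04 | Percent change | Ratio, B = 12 | Percent change | Change for 2 visits per 3 months (B = 13.04) |
|---|---|---|---|---|---|
| Week 12 | 0.92 | −8.0% | 1.00 | 0% | −0.16 |
| Week 16 | 1.23 | +22.7% | 1.33 | +33.3% | +0.45 |
| Week 24 | 1.84 | +84.0% | 2.00 | +100% | +1.68 |

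Conversely, equal counts at baseline and Week 24 require a new rate of B / 24 times the old one. That is 13.04 / 24 = 0.54, a true fall of 46%, or 12 / 24 = 0.50, a fall of 50%.

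**Early termination.** SAP 11.4 assigns visits by actual study day, and the recall period also starts at Day 1, so recall length in days is essentially the study day.
- Week 12 takes Days 71–98 (target 84): at most 84 − 71 = 13 days short, or 15%.
- Week 16 takes Days 99–126 (target 112): at most 13 days short, or 12%.
- Week 24 takes Day 155 onward (target 168): at most 13 days short, or 8%.
- Early termination visits outside these windows fall in Week 4, 8 or 20. Those more than 15 days after last dose go to the follow-up visit. Table 14.2.3.5 reports none of these.

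**Trial visits.** Six scheduled visits fall at Weeks 4 to 24, so up to 6 could enter the other-professional count by Week 24. Screening (Day −28 to Day −1, extendable by up to 4 weeks) lies inside the baseline 3 months. How many subjects would count such visits is unknown.

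**Check of the rate.** Take 2 visits per 13 weeks, unchanged. Baseline: 2 / 13 × 4 = 0.62 visits per 4 weeks. Week 24: the count is 2 × 24 / 13 = 3.69, and 3.69 / 24 × 4 = 0.62. The change is 0, and the same cancellation holds at every visit. If subjects in fact recall 12 weeks at baseline, dividing by 13 leaves a ratio of 13 / 12 = 1.08 at every visit: a small constant offset with no trend.

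**The case against.** The strongest reply is that the plan never tabulates an HEOR change. Protocol 8.7.2, the HEOR item in SAP 12.7.3, the table shell and the listing all stop at by-visit values. A reader might infer from the endpoint definition that a spurious near-doubling will be reported as a change from baseline; no planned table or listing has a row or column for it. What remains is that the definition in both documents still says change from baseline, so definition and output disagree, and the table still presents a 3-month count with 12-, 16- and 24-week cumulative counts without comment.

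A reader might also infer that HEOR cannot be interpreted at all. That goes too far. At a given visit all four randomised arms answer over the same nominal window, so the comparison with placebo largely stands. At Week 12 the windows differ by about a week or not at all, and cumulative answers can be differenced within a subject.

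Two further inferences are weaker than they look. Early terminators do not bring very short recall periods into the reported visits, because the SAP windows cap the shortfall at 13 days; the looser closest-visit rule in Protocol 8.7.3 yields to the SAP under Protocol 8.10. Trial visits need not contaminate the counts irretrievably, because the reason for every visit is collected and listed.

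Finally, HEOR is descriptive, with no test and no imputation. That limits the weight of the point but does not make the counts comparable.

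**Conclusion.** The point holds for within-arm change and time course. With constant use, the raw count relative to baseline is about 0.92, 1.23 and 1.84 at Weeks 12, 16 and 24, or 1.00, 1.33 and 2.00 if 3 months is taken as 12 weeks. The Week 12 distortion is slight; those at Weeks 16 and 24 are material. The ratios rest on a constant visit rate and on visits held at their nominal weeks, and do not depend on how high the rate is. The uneven treatment of trial visits is a secondary problem of unknown size. Same-visit comparisons between arms are largely unaffected, and neither co-primary conclusion is touched. The correction is worth making because it is cheap and because the stated endpoint and the planned table do not agree.

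**What to change.** In SAP 12.7.3 and Table 14.2.3.5:

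1. Derive visits per 4 weeks for each question: baseline count / 13 × 4, and post-baseline count / weeks from first dose to the visit × 4. SAP 11.2 already supplies Day 1, with a fallback when the first-dose date is missing.
2. Report by-visit values, and any change from baseline, on this rate only.
3. Reconcile the endpoint definition with the table: either add a change row on the rate scale or define HEOR as a by-visit summary.
4. Use the stated reasons to remove trial visits, including Screening at baseline, from all three counts.
5. Footnote that the post-baseline windows are cumulative and overlap, so successive rates are not independent periods.

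The cost is one derived variable, a review of the reason text and a table edit, with no new data. Rewording the questionnaire is optional and not needed for this fix. It may also be too late: the protocol's planned dates end in January 2019 and the SAP amendment is dated April 2019.
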